### 3. OBJECTIVES AND ENDPOINTS

Objectives	Endpoints
Primary – Phase 2	

 
To select maximally tolerated dose for use in Phase 3, and to assess the effect of dociparstat on disease progression in participants with severe COVID-19
 
	
 
Incidence of AEs, severe AEs, and SAEs
 
Proportion of participants who are alive and free of invasive mechanical ventilation through Day 28
 

Primary – Phase 3	

 
To assess the effect of dociparstat on disease progression in participants with severe COVID-19
 
	
 
Proportion of participants who are alive and free of invasive mechanical ventilation through Day 28
 

Key Secondary	

 
To assess the effect of dociparstat on mortality
 
	
 
All-cause mortality through Day 28
 

Secondary	

 
To determine additional evidence of a therapeutic effect of dociparstat in participants with severe COVID-19
 
	
 
Time to invasive mechanical ventilation or all-cause mortality
 
Time to all-cause mortality
 
Proportion of participants who are alive, discharged from the hospital, and not using home oxygen at fixed time points (Days 8, 14, and 28)
 
Clinical status assessed by the NIAID ordinal scale at fixed time points (Days 8, 14, and 28)
 
Time to clinical improvement, defined as time to at least a 2-grade improvement from baseline on the NIAID ordinal scale
 
Number of ventilator-free days from baseline through Day 28
 
Time to hospital discharge
 
Time to resolution of fever, defined as temperature <math>\leq 99.0^{\circ}\text{F}</math> (<math>\leq 37.2^{\circ}\text{C}</math>) and no antipyretic use within the preceding 48 hours (participants with baseline fever only)
 
Change from baseline in C-reactive protein level
 
Change from baseline in serum ferritin level
 
Change from baseline in lactate dehydrogenase level
 
Change from baseline in d-dimer level
 
Daily average of prednisone-equivalent corticosteroid dose through Day 28
 

Objectives	Endpoints

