### 7.1. Interruption of Study Intervention

Infusion of study intervention (i.e., dociparstat or placebo) will be interrupted in the following situations:

**aPTT:** If aPTT is >50 seconds, repeat testing as soon as practicable. If aPTT is confirmed >50 seconds (or when retest and confirmation cannot occur within the same day), reduce the dose of enoxaparin or unfractionated heparin (as applicable). If aPTT remains elevated upon repeat testing, then interrupt the study intervention infusion. [Note: ensure aPTT samples were not obtained from the same line as the study intervention infusion (e.g., collect samples via peripheral venipuncture).]

- Participants in cohorts with dociparstat dosed at 0.25 mg/kg/hr: study intervention dosing will not be resumed if interruption criteria are met.
- Participants in cohorts with dociparstat dosed at 0.325 mg/kg/hr: To minimize time that the participant is off therapy, perform repeat testing for aPTT approximately 2 to 6 hours after interruption (as practicable). When aPTT is <40 seconds, the infusion may be resumed at a reduced dose of 0.25 mg/kg/hr.

**Renal function:** If the calculated creatinine clearance drops below 30 mL/min or eGFR drops below 30 mL/min/1.73 m^2 prior to or during dosing with study intervention, the infusion will be held until the creatinine clearance or eGFR rises to  $\geq 30$ .

**Thrombocytopenia:** If a participant experiences a decrease in platelet count by  $\geq 50\%$  from baseline value, or has an absolute platelet count of  $<50,000/\text{mm}^3$  they are to be evaluated for possible HIT, per the algorithm in [Appendix 6](#).

Consistent with the mechanism of dociparstat, no evidence of HIT has been identified in clinical studies. However, considering the risk of HIT associated with potential concomitant medications used for venous thromboembolism (VTE) prophylaxis during study participation, it is recommended that investigators evaluate participants for HIT if they meet platelet criteria described above, starting with assessment of the 4Ts score to determine pretest probability, and proceeding with testing per the algorithm for participants who score  $\geq 4$  (considered intermediate or high pretest risk of HIT).

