## 7.2. Discontinuation of Study Intervention

In some instances, it may be necessary for a participant to permanently discontinue study intervention before completing the protocol-specified treatment period. Reasons for permanent discontinuation of study intervention may include the following:

- Criteria for restarting study intervention after interruption were not met.
- ALT  $\geq 3$ x ULN (and  $>2$ x baseline value) plus bilirubin  $\geq 2$ x ULN.
- Thrombocytopenia defined as a platelet count of  $<30,000/\text{mm}^3$ .
- Hemorrhagic AE of Grade 3 or higher (graded according to the National Cancer Institute-Common Terminology Criteria for Adverse Events [NCI-CTCAE]).
- Other treatment-related AE of unacceptable severity.
- Condition has improved and participant is eligible for hospital discharge.
- Participant requests to discontinue study intervention.
- Investigator initiates treatment with a therapeutic anticoagulant dose, a thrombolytic agent, or otherwise prohibited therapy that may affect the participant's safety if study intervention were to be continued.
- Investigator determines discontinuation is in the best interests of the participant for safety, behavioral, compliance, or administrative reasons.

Participants who discontinue study intervention early will complete the early discontinuation assessments (refer to the Schedule of Assessments) and will continue to be followed-up through Day 28.

Note: For participants who are discharged from the hospital prior to Day 8, the next visit will be Day 14.

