##### **9.4.3.1. Adverse Events**

Treatment-emergent AEs are those that begin on or after the date of the first dose of study intervention.

Summaries (number and percent of participants) of treatment-emergent AEs (by system organ class and preferred term) will be provided as follows:

- All
- Severe, life-threatening, and fatal
- Treatment-related
- Severe, life-threatening, and fatal treatment-related
- Serious

- Treatment-related serious
- Those leading to study intervention discontinuation
- Those leading to study intervention interruption
- Fatal

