1	xx (xx.x)	xx (xx.x)	xx (xx.x)	xx (xx.x)
2	xx (xx.x)	xx (xx.x)	xx (xx.x)	xx (xx.x)
3	xx (xx.x)	xx (xx.x)	xx (xx.x)	xx (xx.x)
4	xx (xx.x)	xx (xx.x)	xx (xx.x)	xx (xx.x)
5	xx (xx.x)	xx (xx.x)	xx (xx.x)	xx (xx.x)
6	xx (xx.x)	xx (xx.x)	xx (xx.x)	xx (xx.x)
7	xx (xx.x)	xx (xx.x)	xx (xx.x)	xx (xx.x)

N = Number of subjects in a specific group; n = Number of subjects with data available; Percentages are based on N;
Infusion (days received): Study drug administered at any time during the corresponding study-day (cumulated).

Page X of Y

Table 4: Listing of study drug interruptions / discontinuations - Safety Set

Subject Age/Sex/Race	Treatment Group	Visit	Start Date / Time	Stop Date / Time	Bolus / Infusion no	Total Voulume Given (mL)	Interrupted due to	Permanently discontinued due to
999-999 / 69/F/W	DSTAT 0.25	Baseline (D1)	ddMMMyy hh:mm	ddMMMyy hh:mm	Bolus	999.99	Adverse Event	
		Day 2 (D2)	ddMMMyy hh:mm	ddMMMyy hh:mm	1	999.99		
		Day 3 (D3)	ddMMMyy hh:mm	ddMMMyy hh:mm	2	999.99	Other:xxxxxx	Adverse Event
		Day 4 (D4)	ddMMMyy hh:mm	ddMMMyy hh:mm	3	999.99		Other: xxxxxx
					4	999.99		
999-999 / 35/M/B	Cohort 1 PBO	Baseline (D1)	ddMMMyy hh:mm	ddMMMyy hh:mm	Bolus	999.99	Adverse Event	
			ddMMMyy hh:mm	ddMMMyy hh:mm	1	999.99		
		Day 2 (D2)	ddMMMyy hh:mm	ddMMMyy hh:mm	2	999.99		

Page X of Y

(Note for programmer: Sorted by subject number, start date, start time)

Table 5: Treatment disposition - Safety Set

Treatment disposition	DSTAT 0.25 N=xxx	Cohort 1 PBO N=xxx	DSTAT 0.325 N=xxx	Cohort 2 PBO N=xxx
Primary reason for treatment discontinuation				
Completed treatment, n(%)	xx (xx.x)	xx (xx.x)	xx (xx.x)	xx (xx.x)
Treatment disposition unknown, n(%)	xx (xx.x)	xx (xx.x)	xx (xx.x)	xx (xx.x)
Discontinued treatment, n(%)	xx (xx.x)	xx (xx.x)	xx (xx.x)	xx (xx.x)
Primary reason for treatment discontinuation, n(%)				
Progression of disease	xx (xx.x)	xx (xx.x)	xx (xx.x)	xx (xx.x)
Adverse Event	xx (xx.x)	xx (xx.x)	xx (xx.x)	xx (xx.x)
Patient requires use of a prohibited therapy	xx (xx.x)	xx (xx.x)	xx (xx.x)	xx (xx.x)
Non-compliance	xx (xx.x)	xx (xx.x)	xx (xx.x)	xx (xx.x)
Lost to follow-up	xx (xx.x)	xx (xx.x)	xx (xx.x)	xx (xx.x)
Patient withdrawal of consent	xx (xx.x)	xx (xx.x)	xx (xx.x)	xx (xx.x)
Physician decision	xx (xx.x)	xx (xx.x)	xx (xx.x)	xx (xx.x)
Sponsor decision	xx (xx.x)	xx (xx.x)	xx (xx.x)	xx (xx.x)
Improvement of condition under study	xx (xx.x)	xx (xx.x)	xx (xx.x)	xx (xx.x)
Other	xx (xx.x)	xx (xx.x)	xx (xx.x)	xx (xx.x)

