Table 9: Severe, life-threatening or fatal treatment emergent Adverse Events - Safety Set

For the layout refer to Table 8

(Notes for programmer:

- Change first line in the table to "Number (%) of subjects with at least one such AE".
- TEAEs with the following AE severity grades are reported: Grade 3 (Severe), Grade 4 (Life-threatening), Grade 5 (Fatal)..)

Table 10: Treatment emergent Adverse Events leading to study drug discontinuation - Safety Set

For the layout refer to Table 8

(Note for programmer: Change first line in the table to "Number (%) of subjects with at least one such AE".

Table 11: Serious treatment emergent Adverse Events - Safety Set

For the layout refer to Table 8

(Note for programmer: Change first line in the table to "Number (%) of subjects with at least one such TEAE".

Table 12: Listing of Serious Adverse Events and Adverse Events of Special Interest - Safety Set

Subject Age/Sex/Race	Treatment Group	Preferred term Verbatim	Start Date (Study Day)	Stop Date (Study Day)	Severity	Relationship	Serious AE	AE of Special Interest	Action taken with study drug	
999-999 / 70/F/W	DSTAT 0.25	PT1xxxxxxxx	DdMMMyy (xx)	DdMMMyy (xx)	Mild	Related	Fatal	Yes	Yes	Discontinued
999-999 / xx/xx/xx	Cohort 1 PBO	PT1xxxxxxxx	DdMMMyy (xx)	DdMMMyy (xx)	Mild	Related	Recovered	No	Yes	No Change

Note: Adverse events are coded using MedDRA version 23.0.

Study Days prior to first treatment date are calculated as (actual date - first treatment date), after first treatment date as (actual date - first treatment date) + 1.

Page 1 of x

(Notes for programmer:

- Sorted by subject number, start date, stop date, Preferred term and Verbatim
- Outcome: Ongoing=Not recovered (Ongoing), Sequelae=Recovered with Sequelae, Unknown=Unknown/Lost to Follow-up
- Action taken with study drug: Interrupted=Study drug temporarily interrupted, Discontinued=Study drug permanently discontinued

Table 13: Overview CTCAE v5.0 Grades

Parameter	Grade 1	Grade 2	Grade 3	Grade 4
Hemoglobin	<LLN - 10.0 g/dL <LLN - 6.2 mmol/L <LLN - 100 g/L	<10.0 - 8.0 g/dL <6.2 - 4.9 mmol/L <100 - 80g/L	<8.0 g/dL <4.9 mmol/L <80 g/L	NA
Platelets		<LLN - 75,000/mm ³ ; <LLN - 75.0 x 10 ⁹ /L	<75,000 - 50,000/mm ³ ; <75.0 - 50.0 x 10 ⁹ /L	<50,000 - 25,000/mm ³ ; <50.0 - 25.0 x 10 ⁹ /L
Activated Partial Thromboplasting Time (aPTT)	>ULN - 1.5 x ULN	>1.5 - 2.5 x ULN	>2.5 x ULN	NA
Prothrombin Intl. Normalized Ratio (INR)	>1.2 - 1.5	>1.5 - 2.5	>2.5	NA

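### SAP Tables 5 and 10 count permanent discontinuations only, so they can understate aPTT-triggered stops at 0.325 mg/kg/hr relative to 0.25 mg/kg/hr

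*SAP*

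**What the plan says.** **The rule differs by cohort.** Protocol 7.1 (repeated in the synopsis) uses one aPTT trigger with two consequences. For the lower dose: "Participants in cohorts with dociparstat dosed at 0.25 mg/kg/hr: study intervention dosing will not be resumed if interruption criteria are met". For the higher dose: "When aPTT is <40 seconds, the infusion may be resumed at a reduced dose of 0.25 mg/kg/hr". Protocol 7.2 counts an interruption that never meets its restart criteria as a reason for permanent discontinuation: "Criteria for restarting study intervention after interruption were not met".

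**The protocol plans two summaries.** Section 9.4.3.1 lists a treatment-emergent AE summary for events leading to discontinuation and a separate one: "Those leading to study intervention interruption".

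**The SAP has shells for one of them.**
- Table 10 is "Table 10: Treatment emergent Adverse Events leading to study drug discontinuation - Safety Set". No table covers interruption.
- The programmer notes to Table 12 keep the two outcomes apart: "Action taken with study drug: Interrupted=Study drug temporarily interrupted, Discontinued=Study drug permanently discontinued".
- Table 5 has rows for completed, unknown and "Discontinued treatment, n" (%), and none for interruption.
- Table 3 counts a day as dosed if any drug ran that day.
- Interruptions appear in the Table 4 listing, with reason, start and stop times and volume, and as an action taken in the Table 12 listing for SAEs and AEs of special interest.

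**Use of the outputs.** SAP section 2 says the first part of the analysis (section 5.1) is equivalent to the DMC output for Cohort 2. The DMC advises on the Cohort 3 dose from Cohort 1 and 2 safety data (protocol 9.6), and Phase 3 uses the Cohort 3 dose. The Phase 2 objective begins: "To select maximally tolerated dose for use in Phase 3".

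**The concern.** Suppose a participant in each cohort meets the aPTT interruption criteria on Day 2. In the 0.25 cohort that participant counts as discontinued in Table 5, and in Table 10 if the aPTT rise is recorded as an AE. In the 0.325 cohort the participant may restart, finish the week and count as having completed treatment, with no summary row showing that a stop occurred or that the rest of the infusion ran at the reduced rate. The same event is counted at one dose and may go uncounted at the other. A reader who compares discontinuation percentages across the two dose columns would then see a difference that comes partly from the restart rule. These tables sit in the package used to advise on the dose, where aPTT prolongation is a stated consideration (protocol 4.3).

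**Working it through.** **Step 1. What each output shows for an aPTT-triggered stop**

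| Output | 0.25 cohort | 0.325 cohort, restarted |
|---|---|---|
| Table 5 | discontinued | completed, if the week is finished |
| Table 10 | counted, if recorded as an AE | not counted |
| Table 3 | fewer days | each day with any drug counts; rate not shown |
| Table 4 (listing) | shown | shown, with reason and times; no rate column |
| Tables 8, 9, 11, 14, 16 | do not depend on the label | do not depend on the label |

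Table 14 does not isolate the 50-second trigger. If ULN is 35 seconds (the upper boxplot reference limit in the SAP), Grade 1 runs to 1.5 × 35 = 52.5 seconds. Table 16 shows only whether values lie below, within or above the normal range.

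**Step 2. Direction**

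Let p1 and p2 be the true aPTT-stop rates at 0.25 and 0.325, and r the share of stops at 0.325 that restart. The tables show p1 at 0.25 and p2 × (1 − r) at 0.325. For any r above 0 the higher dose is understated by the factor (1 − r). At r = 0 there is no distortion.

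**Step 3. Size, as an illustration**

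The documents give no p1, p2 or r, so there is no figure of the plan's own to reproduce. Inputs:
- Active participants at 0.25: 6 (protocol 4.1).
- Active participants at 0.325: 8 (protocol 4.1) or 6 (SAP section 2); the two conflict.
- p1 = p2 = 5%, 10% or 20%, and r = 2/3: assumptions.

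With X ~ Bin(6, p1) and Y ~ Bin(n2, q), the chance that 0.325 shows the lower percentage is the sum over i of P(X = i) × P(Y/n2 < i/6). Put q = p2 if every stop is counted, and q = p2 × (1 − r) for the tables as planned.

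Worked case, 20%, n2 = 8, q = 0.20 × 1/3 = 0.0667:
0.3932 × 0.9049 + 0.2458 × 0.9871 + 0.0819 × 0.9989 + 0.0154 + 0.0015 + 0.0001 = 0.70.

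The same case with every stop counted, q = 0.20:
0.3932 × 0.5033 + 0.2458 × 0.7969 + 0.0819 × 0.9437 + 0.0153 + 0.0015 + 0.0001 = 0.49.

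| Equal stop rate | n2 | Every stop counted | Permanent stops only |
|---|---|---|---|
| 5% | 8 | 0.25 | 0.26 |
| 10% | 8 | 0.40 | 0.46 |
| 20% | 8 | 0.49 | 0.70 |
| 20% | 6 | 0.35 | 0.59 |

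At low rates the shift is small because ties dominate: at 5%, both arms show zero stops with probability 0.95^14 = 0.49 even when every stop is counted. With unequal assumed rates of 20% at 0.25 and 40% at 0.325, half restarting and n2 = 8, the chance moves from 0.18 to 0.49.

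**The case against.** The strongest reply is that the information is in the package. Table 4 lists every interruption with its reason and times. Table 15 lists aPTT by participant, and Figure 3 plots it. With 6 + 8 = 14 active participants (12 on the SAP's numbers), the DMC can count interruptions by hand. After an aPTT stop only one restart rate is allowed, so a resumed infusion in Table 4 implies its rate. All of this stands. It limits the harm, but it does not supply the summary that the protocol planned.

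A reader might infer that the tolerability tables as a whole, or the dose decision itself, are biased toward 0.325. The documents do not support that. The Phase 2 safety endpoints are AEs, severe AEs and SAEs, and their tables do not depend on whether a stop is called an interruption or a discontinuation. No passage bases dose selection on Table 5 or Table 10. The rule is set by cohort under blinding, so comparisons of dociparstat with placebo within a cohort are not distorted.

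A reader might also infer that results in the 0.325 column cannot be attributed to 0.325. That goes too far. The step-down is part of the regimen as written for that dose, and completion under each regimen is a legitimate quantity. What is missing is any summary of how much infusion ran at each rate.

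High stop rates cannot be presumed either. The trigger takes several steps (aPTT above 50 seconds, a retest, a heparin or enoxaparin reduction, then still elevated), and entry excludes aPTT above 42 seconds. The protocol describes the aPTT effects seen earlier as modest. None of this fixes a rate, but it is why the lower rates belong in the table above.

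Finally, this SAP covers only the post-Cohort 1 or 2 lock analysis, and it omits some other AE summaries from 9.4.3.1. The interruption table may therefore be meant for the later Phase 2 SAP. It would still be absent from the output equivalent to the DMC package.

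**Conclusion.** The point holds for Tables 5 and 10 read across doses. They can understate aPTT-related stops at 0.325 relative to 0.25, and the interruption summary planned in protocol 9.4.3.1 has no shell. The direction follows from the documents whenever at least one participant restarts. The size does not: it is nil with no restarts, negligible at 5% stop rates and material at 20%, all under an assumed two-thirds restart share. This is a cheap reporting improvement that removes a directional distortion from one comparison. It does not show that dose selection is biased.

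**What to change.** Change outputs only; no position is taken on the stopping or restart rule.

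1. Add the by-arm table of treatment-emergent AEs leading to study drug interruption that protocol 9.4.3.1 plans, in the Table 8 layout.
2. Add to Table 5 one row for any aPTT-triggered stop, counted identically in both cohorts and split into resumed at reduced rate and not resumed.
3. Add to Table 3 the infusion time at the assigned rate and at the reduced rate.
4. Reconcile the Cohort 2 allocation: SAP section 2 gives 6:6, while protocol 4.1 gives 8:4 and the same SAP section cites the change to 2:1.

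The cost is one extra table and a few rows. The eCRF already collects start and stop times (protocol 6.5) and reasons for interruption (protocol 7), so no new participants or procedures are needed. The downside for the sponsor is that the tolerability figure for the higher dose may look less favourable.

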Aspartate Aminotransferase (AST)	>ULN - 3.0 x ULN	>3.0 - 5.0 x ULN	>5.0 - 20.0 x ULN	>20.0 x ULN
Alanine Aminotransferase (ALT)	>ULN - 3.0 x ULN	>3.0 - 5.0 x ULN	>5.0 - 20.0 x ULN	>20.0 x ULN
Total Bilirubin	>ULN - 1.5 x ULN	>1.5 - 3.0 x ULN	>3.0 - 10.0 x ULN	>10.0 x ULN
Creatinine	>ULN - 1.5 x ULN	>1.5 - 3.0 x ULN	>3.0 - 6.0 x ULN	>6.0 x ULN
Creatinine Clearance, Estimated	<LLN - 60 ml/min	<60 - 30 ml/min	<30 - 15 ml/min	<15 ml/min

NA = Not applicable, ULN = Upper limit of normal, LLN = Lower limit of normal.

Grade 0 : Any result not graded 1, 2, 3, 4 or Unknown.

Grade Unknown : Missing result or missing upper limit of normal for parameters requiring ULN for grading.

(Notes for programmer:

- LLN for creatinine clearance is fixed 90 mL/min
- Calculation of creatinine clearance (CC) (Cockcroft-Gault):

$$(140 - \text{age (years)})$$

$$CC \text{ (ml/min)} = \frac{140 - \text{age (years)}}{0.8143 \times \text{serum creatinine (}\mu\text{mol/L)}} \times \text{baseline weight (kg)} \times (0.85 \text{ if female})$$

)

Table 14: Distribution of laboratory grade by parameter and visit - Safety Set

Parameter: <Hemoglobin> <Platelets> <Activated partial thromboplastin time (aPTT)> <Prothrombin International Normalized Ratio (INR)> <Aspartate aminotransferase (AST)> <Alanine aminotransferase (ALT)> <Total bilirubin> <Creatinine> <Creatinine Clearance, Estimated >

Scheduled Visit Grades (a)	DSTAT 0.25 N=xxx	Cohort 1 PBO N=xxx	DSTAT 0.325 N=xxx	Cohort 2 PBO N=xxx
Baseline				
Grade 0	xx (xx.x)	xx (xx.x)	xx (xx.x)	xx (xx.x)
Grade 1	xx (xx.x)	xx (xx.x)	xx (xx.x)	xx (xx.x)
Grade 2	xx (xx.x)	xx (xx.x)	xx (xx.x)	xx (xx.x)
Grade 3	xx (xx.x)	xx (xx.x)	xx (xx.x)	xx (xx.x)
Grade 4	xx (xx.x)	xx (xx.x)	xx (xx.x)	xx (xx.x)
Unknown	xx (xx.x)	xx (xx.x)	xx (xx.x)	xx (xx.x)
Maximum Post-baseline Grade				
Grade 0	xx (xx.x)	xx (xx.x)	xx (xx.x)	xx (xx.x)
Grade 1	xx (xx.x)	xx (xx.x)	xx (xx.x)	xx (xx.x)
Grade 2	xx (xx.x)	xx (xx.x)	xx (xx.x)	xx (xx.x)
Grade 3	xx (xx.x)	xx (xx.x)	xx (xx.x)	xx (xx.x)
Grade 4	xx (xx.x)	xx (xx.x)	xx (xx.x)	xx (xx.x)
Unknown	xx (xx.x)	xx (xx.x)	xx (xx.x)	xx (xx.x)

N = Number of subjects in a specific group; n = Number of subjects with data available; Percentages are based on N; (a) CTCAE v5.0 grades using absolute thresholds without accounting for baseline.

Baseline value is defined as the last non-missing measurement prior to, or on the date/time of the first administration of study treatment.

NA = not applicable

Page X of Y

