(Notes for programmer:

- CTCAE Grades: Unknown: missing result (or missing upper limit of normal for parameters requiring ULN for grading). Grade 0: any result not graded 1, 2, 3, 4 or Unknown.
- display only for visit Baseline and Maximum Grade per subject and all 6 categories (Grade 0 - Grade 4 and Unknown), if applicable.
- generate a post-baseline Maximum Grade per subject (incl. unscheduled measurements)
- for the generation of Maximum Grade use the following order: Unknown - Grade 0 - Grade 1, ..., Grade 4)
- Calculation of creatinine clearance (CC) (Cockcroft-Gault):
(140 - age (years))

CC (ml/min) = ----- * baseline weight (kg) * (0.85 if female)
0.8143 * serum creatinine (μmol/L)

)

Table 15: Listing of laboratory results - Safety Set

Subject Age/Sex/Race	Treatment Group	Parameter	Date/Time	Visit	Value \$	Unit	Lower Limit	Upper Limit	Grade (a)	
999-999 70/F/W	DSTAT 0.25	Hemoglobin	Ddmmmyy/mm:hh	Screening	99999 H	NCS	Unit	LLL	UUU	1
			Ddmmmyy/mm:hh	Baseline	99999 L	CS	Unit	LLL	UUU	4

(a) CTCAE v5.0 grades using absolute thresholds without accounting for baseline. Grade=0 and Grade=Unknown are not displayed.
\$: H = Above upper limit of normal; L = Below lower limit of normal, NCS = Not clinically significant, CS= Clinically significant.
Visit "Early Tx DC (TXDC)" denotes Early Treatment Discontinuation Visit.

(Notes for programmer:

- Sorted by subject number, Parameter, date and time
- The following parameter will be displayed: Hemoglobin, platelets, activated partial thromboplastin time (aPTT), prothrombin time (PT), prothrombin international normal ratio (INR), d-dimer, Anti-Xa, aspartate aminotransferase (AST), alanine aminotransferase (ALT), total bilirubin, creatinine, Creatinine Clearance, Estimated.
- LLN for creatinine clearance is fixed 90 mL/min
- CTCAE Grades: reference Table 13.)

Table 16: Shift-table of laboratory results - Safety Set

Parameter: <Hemoglobin> <Platelets> <Activated partial thromboplastin time (aPTT)> <prothrombin time (PT)> <Prothrombin International Normalized Ratio (INR)> <d-dimer> <Anti-Xa> <Aspartate aminotransferase (AST)> <Alanine aminotransferase (ALT)> <Total bilirubin> <Creatinine> <Creatinine Clearance, Estimated>

DSTAT 0.25 N=xxx				Cohort 1 PBO N=xxx				Baseline (D1)				DSTAT 0.325 N=xxx				Cohort 2 PBO N=xxx																										
<LLN			Normal	>ULN			<LLN			Normal	>ULN			<LLN			Normal	>ULN			<LLN			Normal	>ULN																	
Post-Baseline																																										

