- display for: Hemoglobin, Platelets, Activated partial thromboplastin time (aPTT), prothrombin time (PT), Prothrombin International Normalized Ratio (INR), d-dimer, Anti-Xa, Aspartate aminotransferase (AST), Alanine aminotransferase (ALT), Total bilirubin, Creatinine, Creatinine Clearance, Estimated
- Include reference lines for each parameter in the Box-Whisker-Plot based on the table below. Use the last column "Proposed Reference Range for Boxplots".

Given that normal ranges for laboratory values vary from center to center, we propose standard reference lines be added to the boxplots based on ranges available from the American Board of Internal Medicine (January 2020). Specifically, we will implement this approach according to the ranges noted in the table below without objection. It should be noted that these ranges do not necessarily represent "values of concern" in this population but will give some context to the results relative to a normal population.

Test	ABIM Reference Range	Proposed Reference Range for Boxplots
Hemoglobin	Female: 120-160 g/L Male: 140-180 g/L	120-180 g/L
Platelets	150-450 10 ⁹ /L	150-450 10 ⁹ /L
aPTT	25-35 sec	25-35 sec
PT	11-13 sec	11-13 sec
PT-INR*	n/a	0.8-1.2
D-dimer	<0.5 mg/L	0-0.5 mg/L
Anti-Xa	0.3-0.7 IU/mL	0.3-0.7 IU/mL
AST	10-40 U/L	10-40 U/L
ALT	10-40 U/L	10-40 U/L
Total Bilirubin	5.13-17.10 umol/L	5.13-17.10 umol/L
Creatinine	Female: 44.21-97.26 umol/L Male: 61.89-114.95 umol/L	44.21-114.95 umol/L
Creatinine Clearance	90-140 mL/min/1.73m ²	90-140 mL/min

* Upper reference corresponds to lowest CTCAE Grade 1 result; lower reference from Medline

Table 17: Listing of Prior and Concomitant Medications (only Targeted Medications) - Safety Set

Subject Age/Sex/Race	Treatment Group	ATC Level 2/ Preferred Term/ Medication Name	Start Date (Study Day)	Stop Date (Study Day)	Dose [Unit]	Frequency	Route	Indication
999-999 / 70/F/W	DSTAT 0.25	ATC Level 2 Preferred Term Medication Name	DdMMMyy (xx)	DdMMMyy (xx)	40 [mg]	BID	IV	AE: xxxxxxxxxxxxxxx AE: xxxxxxxxxxxxxxx AE: xxxxxxxxxxxxxxx
999-999 / xx/xx/xx	Cohort 1 PBO	ATC Level 2 Preferred Term Medication Name	DdMMMyy (xx)	Ongoing			PBO	MH: xxxxxxxxxxxxxxx MH: xxxx
999-999 / xx/xx/xx	Cohort 1 PBO	ATC Level 2 Preferred Term Medication Name	DdMMMyy (xx)	Ongoing			PBO	PR: xxxxxxxx

Note: Medications are coded using WHO-DD Version March 2020.

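### Table 14 can show Grade 0 when a local limit is missing: Unknown omits a missing lower limit, and any other graded result hides an Unknown in the maximum

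*SAP*

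**What the plan says.** The grading rules are in SAP Section 5.1.

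- **Ungradable results.** Under Table 13: "Grade Unknown : Missing result or missing upper limit of normal for parameters requiring ULN for grading". The programmer notes to Table 14 repeat this, again naming only the upper limit: "CTCAE Grades: Unknown: missing result (or missing upper limit of normal for parameters requiring ULN for grading".
- **Residual category.** "Grade 0 : Any result not graded 1, 2, 3, 4 or Unknown".
- **Ranking for the post-baseline maximum.** "for the generation of Maximum Grade use the following order: Unknown - Grade 0 - Grade 1, ..., Grade 4".
- **What Table 14 shows.** "display only for visit Baseline and Maximum Grade per subject and all 6 categories (Grade 0 - Grade 4 and Unknown), if applicable". The maximum includes unscheduled measurements.
- **What Table 15 shows.** "Grade=0 and Grade=Unknown are not displayed". Each row does carry the value, both limits, high/low flags and a flag for clinical significance.

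The SAP closes the lower-limit gap for one test only: "LLN for creatinine clearance is fixed 90 mL/min". Protocol Section 8.3.4 requires sites to enter the relevant reference ranges with each result.

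**The concern.** The residual definition makes Grade 0 the default. A result that needs a lower limit for grading, and has none, does not qualify as Unknown, so it drops into Grade 0 with the normal values. A result that lacks an upper limit is handled properly at first. It can then disappear from the summary, because the maximum prefers any graded result, including Grade 0, over Unknown.

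Where either rule changes what Table 14 displays, the change is towards less toxicity. The tests involved matter here. Protocol Section 4.3 names serious bleeding as the primary toxicity of the drug and reports an ALT effect in 37% of dociparstat recipients against 11% on placebo in the COPD study. aPTT also drives the interruption rules in Protocol Section 7.1. SAP Section 2 says the first part of this package is equivalent to the output given to the data monitoring committee for Cohort 2, and that committee makes a recommendation on dosing in Cohort 3.

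**Working it through.** The plan states no figure to reproduce. The check applies the written rules to test values, with and without the limit.

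**Inputs from SAP Table 13**
- Hemoglobin: Grade 1 from the lower limit down to 100 g/L, Grade 2 from below 100 to 80, Grade 3 below 80. Only Grade 1 uses the local limit.
- Platelets: the first band runs from the lower limit to 75 x 10⁹/L; the bands below it are absolute. The column alignment of this row is unclear in the text available to me, so I use the bands and not their grade numbers.
- aPTT: Grade 1 above the upper limit, Grade 2 above 1.5 times, Grade 3 above 2.5 times.
- ALT and AST: Grade 1 above the upper limit, Grade 2 above 3 times, Grade 3 above 5 times, Grade 4 above 20 times. Bilirubin and creatinine are likewise graded only in multiples of the upper limit.
- INR has absolute cut-offs and creatinine clearance has a fixed lower limit, so neither is affected.

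**Assumed limits, for illustration.** Hemoglobin 120 g/L (the lower of the two sex-specific values), platelets 150 x 10⁹/L, aPTT 35 s and ALT 40 U/L. All four appear in the reference table in the Figure 3 notes. The test values are mine.

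**Step 1: lower limit missing**

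| Result | Limit known | Limit missing |
|---|---|---|
| Hemoglobin 110 g/L | Grade 1 | Grade 0 |
| Hemoglobin 100 g/L | Grade 1 | Grade 0 |
| Hemoglobin 99 g/L | Grade 2 | Grade 2 |
| Hemoglobin 79 g/L | Grade 3 | Grade 3 |
| Platelets 149, 100 or 75 | first band | Grade 0 |
| Platelets 74 or 49 | absolute bands | unchanged |

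The gap therefore covers only the first band.

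**Step 2: upper limit missing, single result**
- ALT 400: 400/40 = 10 times the limit, Grade 3. With no limit it is Unknown.
- aPTT 55 s: 55/35 = 1.57 times the limit, Grade 2. With no limit it is Unknown.

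**Step 3: maximum over two post-baseline results, ranked Unknown < 0 < 1 < 2 < 3 < 4**

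| Results | All limits known | Limit missing as marked |
|---|---|---|
| ALT 30 (0.75x), ALT 400 (no limit) | Grade 3 | Grade 0 |
| ALT 60 (1.5x), ALT 400 (no limit) | Grade 3 | Grade 1 |
| aPTT 33 s (0.94x), aPTT 55 s (no limit) | Grade 2 | Grade 0 |
| ALT 300 and ALT 400 (neither with a limit) | Grade 3 | Unknown |

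The last row shows where the plan behaves as intended: with no other graded result, the participant appears in the Unknown row.

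**Step 4: opportunity and scale.** Protocol Table 1 schedules aPTT on Days 2 to 7 and chemistry on Days 2, 4, 6, 8, 14 and 28, six post-baseline samples each. A single result without a limit will therefore usually have a graded one beside it. With planned arms of 4 to 8 in Protocol Section 4.1, one participant is 100/8 = 12.5 to 100/4 = 25 percentage points of a Table 14 cell. That is the weight of one person, not an estimate of how often this occurs.

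**Step 5: the other outputs.** The high/low flags in Table 15 and the classes in Table 16 need the same limits, and Table 16 has no rule for a missing one. Figure 3 plots scheduled visits only. The values, limit columns and clinical-significance flags in Table 15 remain available.

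**The case against.** The case for leaving this alone has real substance.

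- **Missing limits should be uncommon.** Sites must enter the ranges. A default rule for a missing limit is not evidence that limits go missing, and nothing shows that unscheduled results lack them.
- **The listing is readable.** With 12 participants per cohort, Table 15 can be read in full, and an empty limit column beside a value reveals a result without a range. Clinically significant changes are also recorded as adverse events (Protocol Section 8.3.4), and a confirmed aPTT above 50 s sets off the steps in Protocol Section 7.1.
- **Creatinine has a second route.** Estimated clearance is calculated from the same serum value and graded without a local limit.
- **The ranking is defensible.** If Unknown ranked above the grades, one result without a limit could erase an observed Grade 3 or 4.
- **The analysis is descriptive.** No decision rule is tied to Table 14.

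All of this stands and limits the importance of the point. It does not make the displayed grade right. The SAP provides for a missing upper limit, and its own rule can then report that participant as Grade 0.

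A reader might infer more: that any result without a limit becomes normal, or that every missing limit is a misclassification. The documents do not support either. A missing upper limit is shown as Unknown at baseline, and also in the maximum when nothing else is graded. A display error needs an abnormal value that either lies in the first hemoglobin or platelet band or is outranked by another graded result.

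**Conclusion.** The point holds in a limited form and is minor. Two rules can understate toxicity in Table 14. The missing lower-limit clause can show a first-band hemoglobin or platelet result as Grade 0 when it should be ungradable. The ranking can hide an aPTT, AST, ALT, bilirubin or creatinine result that has no upper limit. The second is the more serious, because the hidden value could be Grade 3 or, for tests other than aPTT, Grade 4.

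A reader might also infer that a large fall in hemoglobin or platelets could be lost. It could not: hemoglobin below 100 g/L and platelets below 75 x 10⁹/L are graded on absolute cut-offs.

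The conclusion rests on a literal reading of the definitions and assumes no unwritten programming convention. How often limits are missing is not stated, so the effect on the actual tables cannot be estimated.

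**What to change.** 1. In the Table 13 footnote and the matching Table 14 note, define Unknown as a missing result, or a missing lower or upper limit where that limit is needed to grade the value. Keep the absolute grades for hemoglobin and platelets when the lower limit is missing. A hemoglobin of 100 g/L or more with no lower limit then becomes Unknown.
2. Keep the ranking, so that an observed Grade 1 to 4 is not erased. Add a Table 14 row counting participants with any Unknown post-baseline result. Unknown also covers absent results, so splitting the count into absent result and absent limit would make it easier to read.
3. Print Unknown in the grade column of Table 15, so that a blank means Grade 0 only.

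Grading against the American Board of Internal Medicine ranges should be at most an optional, flagged sensitivity display. The SAP introduces them for plots only ("we propose standard reference lines be added to the boxplots") and notes that normal ranges differ between centers. The 35 s limit would also assign Grade 1 to aPTT values of 36 to 42 s, which the eligibility criteria admit.

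The cost is one extra row (two if the count is split) and two footnote edits. No new data are needed.
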